## ABBREVIATIONS AND DEFINITION OF TERMS

Abbreviation	Definition
ADL	Activities of Daily Living
AE	Adverse Event
SAE	Serious Adverse Event
CRF	Case Report Form
eCRF	Electronic Case Report Form
CTCAE	Common Terminology Criteria for Adverse Events
CR	Complete Response
PR	Partial Response
SD	Stable Disease
PD	Progressive Disease
EIU	Exposure in Utero
FGF	Fibroblast Growth Factor
IRB/IEC	Institutional Review Board/Independent Ethics Committee
MFDS	Ministry of Food and Drug Safety
LPD	Local Product Document
LSLV	Last Subject Last Visit
NCI CTC	National Cancer Institute Common. Terminology Criteria
ODC	Obvious Data Correction
ORR	Objective Response Rate
PCD	Primary Completion Date
PDGF	Platelet-derived Growth Factor

PFS	Progression-free survival
PV	Pharmacovigilance
RCC	Renal Cell Carcinoma
RECIST	Response Evaluation Criteria In Solid Tumors
SAP	Statistical Analysis Plan
SOP	Standard Operating System
SRSD	Single Reference Single Document
TPP	Time to progression
VEGF	Vascular Endothelial Growth Factor

## 1. RATIONALE AND BACKGROUND

Renal cell carcinoma (RCC) accounts for 85% of kidney cancers, and is a collection of different types of tumors that arise from the renal epithelium. Renal cell carcinoma (RCC) is diagnosed in approximately 170,000 patients worldwide annually, resulting in 82,000 deaths.

Early stage disease does not typically produce significant clinical signs or symptoms, consequently 25-30% of newly diagnosed patients present with advanced (including locally invasive or advanced) or unresectable disease. The 5-year survival rate for advanced RCC is estimated to be ≤10%.

Most RCCs are highly vascularised tumors that over-express a number of growth factors, including VEGF (Vascular endothelial growth factor), PDGF (Platelet-derived growth factor) and fibroblast growth factor (FGF). The clear cell RCC subtype represents approximately 85% of the RCC population and frequently displays allelic loss on chromosome 3p, accompanied by mutational inactivation of the von Hippel-Lindau (VHL) tumor suppressor gene. VHL-associated RCC are known for their vascularity and these tumors produce high levels of vascular endothelial growth factor (VEGF). In addition, recent studies suggest that in sporadic clear cell RCC, increased expression of VEGF is closely correlated with neovascularization, which is a prerequisite of tumor growth and metastasis.

INLYTA®, a substituted indazole derivative, is an oral, potent, and selective inhibitor that blocks signal transmission via vascular endothelial growth factor receptor (VEGFR-1, -2 and -3) which is related to vascularization of tumors and tumor proliferation.

INLYTA® was first approved as new medicine on 22 Aug 2012. As required for any new medication approved by Ministry of Food and Drug Safety (MFDS), safety and efficacy information of new medication should be provided at minimum 3000 subjects administered in the setting of routine practice during the initial 6 years after the approval. However, based on MFDS's review upon Pfizer Korea's request, additional 3 years of study period has been granted to collect safety and efficacy information of minimum of 100 subjects.

## **2. RESEARCH QUESTION AND OBJECTIVES**

The objective of this study is to monitor usage of INLYTA® in real practice including adverse events on INLYTA®.

## **3. RESEARCH METHODS**

### **3.1. Study design**

Observational, non-interventional drug and multi-center study in which subjects will be administered as part of routine practice at Korean health care centers by accredited physicians. At least 3000 subjects should be enrolled in this study based on the Article 6 of “Basic Standards for the Re-examination of New Medicines” notified by MFDS. However, with additional 3 years of study period, at least 100 subjects who are being treated with Inlyta within the approved indication will be studied for total of 9 years according to the review result by the MFDS per Pfizer’s request to adjust the number of subjects. The study can be performed in Korean health care centers where INLYTA® is prescribed for advanced renal cell carcinoma (aRCC) after failure of one prior systemic therapy which is the indication for INLYTA® and where post-marketing study is allowed by institutions.

To achieve the target sample size, the study is being conducted in prospective study design and retrospective study design.

Patients to whom INLYTA® is first administered or patients who are already on INLYTA® during the study period should be enrolled in the study. Observation should be done from treatment initiation of INLYTA® for at least 28 calendar days. There are no visits or activities mandated by this study and routine observation will be done during INLYTA® treatment.

### **3.2. Study population**

All subjects enrolled should meet the usual prescribing criteria for INLYTA® as per the Local Product Document (LPD) and should be entered into the study at the physician’s discretion.

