#### **3.5.4. Investigating Matters**

This means that the physician should enroll all subjects to whom INLYTA® is prescribed for the first time after contract is executed and who agree that Pfizer Korea and companies working with Pfizer Korea use his/her information by signing the 'data privacy statement'.

Data for patients who are currently on INLYTA® will be collected as much as possible following the categories for patients who are prescribed with INLYTA® for the first time.

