### 3.5.4.9. Safety

#### 3.5.4.9.1. Adverse Event

Every observed and reported adverse event, regardless of the causal relationship with the study drug, must be recorded on an adverse event section in case report forms. The query pattern of experience of adverse event to the subjects is as follow;

Patients who are prescribed with INLYTA® for the first time during the study period: “Have you had any health problem since last visit?”

Patients who are already on INLYTA® at the time of enrollment: all safety information will be collected from medical chart since the date of treatment initiation.

For adverse events repeating before and after administrating the study drug, record the date adverse event was first experienced and the date adverse event resolved. Background information on INLYTA® can be obtained from the current version of the local product document, which is the single reference safety document (SRSD) for information relating to INLYTA®.

Check either ‘yes’ or ‘no’ in adverse event section. If ‘yes’, record in detail.

- Adverse events: Record the name of adverse event. If possible, specify diagnosis, not individual symptoms. Record the name according to National Cancer Institute Common Terminology Criteria for Adverse Events (CTCAE) Version 5.0.
- Date of onset: Record the date of onset. Record approximate date if an actual date is unknown.
- Date of resolution: Record the date of resolution. Record approximate date if an actual date is unknown.
- Severity: Severity evaluation of adverse event must be done according to the NCI CTC grade.
  - The physician will use the following definitions of severity in accordance with the National Cancer Institute Common Terminology Criteria for Adverse Events (CTCAE) Version 5.0 to describe the maximum intensity of the adverse event:

Grade	Definition
Grade 1	Mild; asymptomatic or mild symptoms; clinical or diagnostic observations only; intervention not indicated.
Grade 2	Moderate; minimal, local or noninvasive intervention indicated; limiting age-appropriate instrumental ADL*.
Grade 3	Severe or medically significant but not immediately life-threatening; hospitalization or prolongation of hospitalization indicated; disabling; limiting self care ADL**.
Grade 4	Life-threatening consequences; urgent intervention indicated.
Grade 5	Death related to AE.

Activities of Daily Living (ADL)

\*Instrumental ADL refer to preparing meals, shopping for groceries or clothes, using the telephone, managing money, etc.

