### **3.6. Power and sample size**

Per MFDS regulation, at least 3000 subjects were required for the study initially. However, based on the decision from MFDS on April 26, 2018, at least 100 subjects who are eligible according to '3.2 Study population' will be observed for total of 9 years

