### **3.9. Data analysis**

Analysis will be performed for the pooled data collected by each investigator during the re-examination period. Total number of centers participating, total number of cases enrolled and retrieved, and total number of cases included in the analysis will be presented in summary tables. Evaluation of data will primarily consist of summary displays (eg, descriptive statistics, tables, and graphs).

Detailed methodology for summary and statistical analyses of data collected in this study will be documented in a Statistical Analysis Plan (SAP), which will be dated, filed and maintained by Pfizer. The SAP may modify the plans outlined in the protocol; any major modifications of primary endpoint definitions or their analyses will be reflected in a protocol amendment.

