2.3. Study Population

All subjects enrolled should meet the usual prescribing criteria for INLYTA® as per the Local Product Document (LPD) and should be entered into the study at the physician's discretion.

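### Two enrolment rules conflict: study entry is left to the physician, yet all consenting first-time users should be enrolled, so selective entry is possible and would go unseen.

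*Protocol*

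**What the plan says.** Protocol 3.2 states that subjects should meet the usual prescribing criteria and "should be entered into the study at the physician’s discretion". SAP 2.3 carries the same clause: "should be entered into the study at the physician's discretion".

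Protocol 3.5.4 gives a different rule for new users: "the physician should enroll all subjects to whom INLYTA® is prescribed for the first time after contract is executed", provided they sign the data privacy statement.

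For existing users, Protocol 3.1 says that "patients who are already on INLYTA® during the study period should be enrolled in the study". It does not say all such patients. The same section explains that, to reach the target number, "the study is being conducted in prospective study design and retrospective study design". For existing users, Protocol 3.5.4.9.1 adds that "all safety information will be collected from medical chart since the date of treatment initiation".

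Protocol 3.6 sets the size by regulatory decision: "at least 100 subjects who are eligible according to '3.2 Study population' will be observed for total of 9 years". On patient accounting, Protocol 3.9 says that "total number of cases enrolled and retrieved, and total number of cases included in the analysis will be presented".

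**The concern.** The objective (Protocol 2) is to monitor use of INLYTA and its adverse events in real practice. The main outputs are AE incidence with 95% confidence intervals (SAP 6.2) and ORR (SAP 6.3). Both describe INLYTA users only if those entered resemble those eligible. A rule to enrol everyone who consents protects that. A rule that leaves entry to the physician does not, since a physician following Protocol 3.2 may leave out an eligible, willing patient for reasons linked to tolerance or prognosis.

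The exposure is greater for patients already on treatment. The 3.5.4 rule covers first prescriptions only, and for existing users that section speaks only of what data to collect. Their chart may already show adverse events and tumor response when the physician decides on entry.

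**Working it through.** **The rules side by side.**

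| Source | Group | Rule | Stated ground for leaving out an eligible patient |
|---|---|---|---|
| Protocol 3.2, SAP 2.3 | All | Entry at discretion | Physician's choice |
| Protocol 3.5.4 | First prescription after contract | All should be enrolled | Patient does not agree to data use |
| Protocol 3.1 | New and existing users | Should be enrolled, without the word all | None stated |

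The first two rows give different answers for an eligible, consenting new user whom the physician prefers not to enter. No section ranks one above the other, and the SAP carries only the discretionary clause. Reading the discretion as one over prescribing does not fit: the sentence concerns entry into the study, and treatment decisions are dealt with in Protocol 3.5.2.

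**Would the outputs show selective entry?** The Protocol 3.9 counts begin with enrolled cases. SAP 3.1, SAP 3.5 and dummy Tables 36 and 37 account for patients removed from the safety set after enrolment. Nothing counts eligible users who were never entered, and Protocol 3.12 does not list selective entry as a limitation.

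**Possible size.** The minimum of 100 has no rate, power or precision behind it, so there is no plan figure to reproduce. The documents give neither outcome rates nor a strength of selection; every input below is an assumption.

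*Illustration 1, omission of higher-risk patients.* Assume 30% of users are higher risk with 40% SAE incidence, and 70% are others with 20%.

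- Full enrolment: 0.70 × 0.20 + 0.30 × 0.40 = 26%.
- One third of the higher-risk patients omitted: (14 + 8)/90 = 24.4%.
- Two thirds omitted: (14 + 4)/80 = 22.5%.
- All omitted: 14/70 = 20.0%.

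*Illustration 2, selection on the outcome itself, in either direction.* Let p be the true rate and r the enrolment probability of patients with the outcome relative to those without it. The expected observed rate is p·r/(p·r + 1 − p). For p = 20% and r = 0.5, this is 0.10/(0.10 + 0.80) = 11.1%. The formula serves equally for AE incidence and ORR.

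| True rate | r = 0.5 | r = 0.8 | r = 1 | r = 1.25 | r = 2 | Exact 95% CI at n = 100 |
|---|---|---|---|---|---|---|
| 20% | 11.1% | 16.7% | 20% | 23.8% | 33.3% | 12.7–29.2% |
| 30% | 17.6% | 25.5% | 30% | 34.9% | 46.2% | 21.2–40.0% |
| 50% | 33.3% | 44.4% | 50% | 55.6% | 66.7% | 39.8–60.2% |
| 80% | 66.7% | 76.2% | 80% | 83.3% | 88.9% | 70.8–87.3% |

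Mild selection (r from 0.8 to 1.25) moves these rates by about 3 to 6 points, inside the interval at 100 patients. Strong selection (r of 0.5 or 2) moves them outside it. With r = 1 there is no shift. The reported interval reflects sampling error only, so it would not widen in any of these cases.

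**The case against.** The best defense is that 3.5.4 is the operational rule and 3.2 a general remark tied to the prescribing criteria, so that sites would in practice enrol everyone. That is possible, but no text says so, and the SAP repeats only the general remark.

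Several stronger readings are tempting, and the documents do not support them.

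- *That every first-time user must be enrolled.* Protocol 3.5.4 says should, and limits the rule to consenting patients first prescribed the drug after the contract.
- *That the results are biased, or biased towards good tolerance.* Nothing shows that selection took place, or in which direction.
- *That there is no directive for existing users.* Protocol 3.1 does direct that they be enrolled; what it lacks is the word all.
- *That sites can pick among finished treatment courses with fully known outcomes.* SAP 3.1 removes from the safety set anyone who completed INLYTA before the contract date, and SAP 3.2 carries this over to the efficacy set. Discretion acts on patients still on treatment, whose outcome is only partly known. The loss of earlier completers is a separate selection, built into the design, and deleting the discretion clause would not cure it.
- *That the analysis offers no protection.* New and existing users are reported separately as well as together (Protocol 3.5.4.1 and 3.9.2, SAP 6.4). Selection among existing users therefore stays out of the new-user estimate. It still affects their own estimate and the pooled one, and selection within either group stays invisible.

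Two practical points also stand. In the first illustration even the extreme case, 20.0%, lies within the exact interval for 26 of 100 (17.7–35.7%). And data collection began in December 2012, with the final report due on 21 November 2021, so past enrolment cannot be redone.

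**Conclusion.** The conflict is real and rests on the text alone: Protocol 3.2 and SAP 2.3 permit what Protocol 3.5.4 does not. Following the discretionary rule can bias AE incidence and ORR, and the planned patient accounting would not reveal it. The documents settle neither direction nor size. The shifts from 26% to between 24.4% and 20.0%, and the wider range in the second illustration, rest wholly on assumed inputs; they show what could happen, not what did. The risk is greater for existing users, and separate reporting contains part of it. This should be corrected, but it does not invalidate the study, and the minimum of 100 is unaffected.

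**What to change.** 1. Delete the discretion clause from Protocol 3.2 and SAP 2.3, so that the 3.5.4 rule governs.
2. For sites and patients still to be enrolled, apply the same rule (all who are eligible and consent) to patients on INLYTA at the contract date.
3. Ask each site for an anonymous count of eligible users not enrolled, with the reason. Collect it going forward, and for past enrolment only where the information exists. Show it beside the enrolment counts of Protocol 3.9.
4. Add two limitations to Protocol 3.12: possible selective entry, and the loss of patients who finished INLYTA before the contract date.

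The cost is a wording change in two places, a rule for existing users, a short addition to the limitations, and a small effort at sites for the count. An aggregate count need not use identifiable data from patients who refused.

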#### **3.2.1. Inclusion criteria**

Subjects must meet all of the following inclusion criteria to be eligible for inclusion in the study:

1. Patients diagnosed as advanced renal cell carcinoma (aRCC) after failure of one prior systemic therapy.
2. Patients to whom INLYTA® is first administered or patients who are already on INLYTA® during the study period
3. Evidence of a personally signed and dated informed consent document indicating that the patient (or a legally acceptable representative) has been informed of all pertinent aspects of the study.

### **3.2.2. Exclusion criteria**

Subjects meeting any of the following criteria will not be included in the study:

1. Any patient who does not agree that Pfizer and companies working with Pfizer use his/her information
2. Patients with hypersensitivity to axitinib or to any other component of INLYTA®
3. Patients under 18
4. Pregnant women

### **3.3. Data sources**

The followings are data sources for the study:

1. Medical records
2. Laboratory test results

### **3.4. Variables**

Variable	Role	Data source(s)	Operational definition
Demographic Characteristics	Baseline characteristics	Medical records	*
Basic Laboratory data	Baseline characteristics	Laboratory test results	*
Concomitant medication	Baseline characteristics	Medical records	*
Efficacy result by physician	outcome	Medical record	*

AE events	outcome	Medical record	*
-----------	---------	----------------	---

\*Refer to 3.5.4.Investigating Matters

Detail instruction of variable will be included Statistical Analysis Plan (SAP) and CRF.

### **3.5. Study procedures**

#### **3.5.1. Study Duration**

As specified in the product license given by MFDS, this study was to be conducted for 6 years from the approval date of 22 Aug 2012 to 21 Aug 2018. On May 2018, MFDS has granted 3 additional years for the study, for total of 9 years for the study period.

#### **3.5.2. Study Treatment**

The use and dosage recommendations for INLYTA® will take place on the basis of the approved LPD and will be adjusted solely according to medical and therapeutic necessity.

#### **3.5.3. Endpoints**

##### **3.5.3.1. Safety Endpoints**

The clinical nature, incidence, duration, and severity of adverse events; discontinuation due to adverse events; outcome and possible causality will be monitored in this study.

##### **3.5.3.2. Efficacy Endpoints**

- Tumor response based on RECIST 1.1
- ORR
- PFS within limited follow-up period
- TTP

#### **3.5.4. Investigating Matters**

This means that the physician should enroll all subjects to whom INLYTA® is prescribed for the first time after contract is executed and who agree that Pfizer Korea and companies working with Pfizer Korea use his/her information by signing the 'data privacy statement'.

Data for patients who are currently on INLYTA® will be collected as much as possible following the categories for patients who are prescribed with INLYTA® for the first time.

#### **3.5.4.1. Reporting of the study**

Final study report will include analysis for patients prescribed with INLYTA® for the first time, for patients who are already on INLYTA® at the time of enrollment, and for all enrolled patients.

#### **3.5.4.2. Demographic Information**

- Name of Institution: Record the name of institution.
- Name of Physician: Record the name of physician engaged into this study.
- Department: Record the medical department, practicing the study.
- Subject ID: Record 4 digit number per subject registration sequence.
- Confirmation of Data Privacy Statement: If all agreement for using subject's personal and medical information, signature and date are obtained by subject or legally authorized representative, then check the box of 'yes'. If not, check 'no' which means that case is excluded from this study.

#### **3.5.4.3. Subject Status**

- Initial of Subject: Record the name of subject with English initials.
- Date of birth: Record the date of birth of the subject.
- Sex: Check either 'male' or 'female'.
- Classification: Check either 'outpatient' or 'inpatient'.
- Height/Weight: Record by cm / kg unit.
- Allergic history: Check either 'yes' or 'no'. If 'yes', then record the allergen and the according symptom.

#### **3.5.4.4. Diagnosis**

- Diagnosis: check the aRCC and classify cell component, 'clear cell' or 'other'.
- Date of diagnosis: Record the date the subject was initially diagnosed as advanced RCC
- Metastasis: Check either 'yes' or 'no'. If 'yes', check the metastasis site. If 'other', specify.
- Primary lesion surgery: Check whether the subject had prior cancer surgery (nephrectomy)

or not. If the subject had the surgical procedure, record the surgical date.

- Prognostic criteria: Record the value of all risk factors for MSKCC and Heng criteria and record the value of serum LDH both at diagnosis and at initiation of treatment of INLYTA (1), (2), (3).

- **MSKCC risk factors**

Karnofsky performance status < 80%
< 1 y between diagnosis and start of first systemic therapy
Corrected serum calcium > 10 mg/dL
Hemoglobin < lower limit of normal
LDH > 1.5 times upper limit of normal

- **Heng risk factors**

Karnofsky performance status < 80%
< 1 y between diagnosis and start of first systemic therapy
Corrected serum calcium > 10 mg/dL
Hemoglobin < lower limit of normal
Neutrophils > upper limit of normal
Platelets > upper limit of normal

### **3.5.4.5. Medical History**

Check the box next to 'yes' or 'no' for past/present disease. If 'yes', record the full name of the disease as appears in the medical terminology dictionary (written by the Korean Medical Science Association). then select the box next to 'past' or 'present' in the line of according disease category. If the disease does not exist in the form, record the full name of the disease in the 'others' category as appears in the medical terminology dictionary (written by the Korean Medical Science Association).

### **3.5.4.6. Prior Chemotherapy/Immunotherapy and Radiation Therapy**

Prior to administrating INLYTA®, if the subject received other chemotherapy / immunotherapy or received radiation therapy to treat, advanced RCC, record them. First, check among 'yes', 'no' or 'unknown'. If 'yes', record the followings.

